Research proposal

1. Project title

The effects of different inspiratory pressures on the diaphragmatic thickness fraction and sternocleidomastoid muscle activation in people after stroke

2. Abstract

This study is a cross-sectional study to determine the optimal inspiratory muscle training (IMT) intensity for stroke survivors. Participants will breathe through a pressure threshold inspiratory loading device with varying loads in random order. During the test, accessory inspiratory muscle (sternocleidomastoid muscles) activity will be measured with surface electromyography (sEMG) and diaphragm thickness will be used to assessed with ultrasonography. Repeated-measures ANOVA will be used for statistical analysis to determine the most effective training intensity.

3. Project objectives

Introduction:

Stroke was the second largest cause of global death and disability in 2019 [1]. Direct medical costs for stroke in China was 50 billion yuan (nearly 7.69 billion US dollars) in 2015, and this accounted for the highest medical cost in China [2]. In 2016, the Global Burden of Disease (GBD) study estimated that the lifetime risk of stroke from the age of 25 years was 39.3% in China, which is the highest estimated risk in the world [3]. In 2018, stroke was the third highest disease cause of death, accounting for 1.57 million deaths in China [4].

Stroke not only causes impairment of motor function but can also affect lung function [5]. The lung function (e.g. forced vital capacity (FVC), forced expiratory volume in one second (FEV1), maximal inspiratory pressure (MIP), peak expiratory flow (PEF)) in people after stroke was reported significantly lower than the age and gender-matched healthy adults [6, 7]. Impaired lung function in people after stroke not only leads to high risk of pneumonia, poor functional outcomes and prolonged hospitalization but may also increase mortality [8-10].

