Inspiratory muscle training (IMT) is an intervention designed for improvement of inspiratory muscle (including the diaphragm) strength and endurance in healthy adults and patients suffering from different diseases (e.g. Parkinson, chronic obstructive pulmonary disease, cardiovascular disease) [18-21]. Regarding the IMT training protocol, the commonly reported training intensities varied between 30-80% of MIP in people after stroke [22-24]. Although the diaphragm is the primary inspiratory muscle, the use of IMT may not help improve the diaphragmatic contraction under some circumstances. Previous studies suggested that, in healthy adults and people receiving mechanical ventilation, when inspiratory load exceeds the capacity of the diaphragm (higher than 60% MIP), the accessory respiratory muscle (in particular the sternocleidomastoid muscle) would be activated dramatically, which would increase work of breathing and fatigue [25, 26]. Other studies also reported that high IMT intensity may have the risk to increase the work of breathing thereby leading to fatigue [27] or resulting in a decrease, rather than increase, in surface electromyography signals in diaphragmatic activity [27]. It is postulated that IMT recruits accessory muscles such as sternocleidomastoid rather than diaphragm during the practice [24]. Hence, evaluation of effectiveness of IMT on DTF in people after stroke and further investigation on determining an optimal training protocol including inspiratory effort and training intensity for recruiting diaphragmatic activities in the stroke population are warranted.

Aims of the study:

To determine the optimal training intensity that is associated with the strongest diaphragmic thickening fraction in people after stroke.

Project significance:

Outcomes of this project study will fill the existing knowledge gaps in the understanding of the relationship between inspiratory pressure and recruitment of diaphragmatic muscles in people after sub-acute and chronic stroke.

4. Research methodology

Study design:

This study will be a cross-sectional study.

Participants:

Individuals who have had a stroke and healthy adults will be invited to participate in this study.

Participants recruitment for people after stroke:

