The inclusion criteria are: (1) age \geq 18 years; (2) clinically diagnosed with ischemic and/or hemorrhagic stroke; (3) duration of stroke range from 1 month to 12 months after diagnosis; (4) had no facial palsy, which could prevent proper labial occlusion; (5) had not undergone thoracic or abdominal surgery; (6) could understand and follow the verbal instruction; (7) stable cardiac conditions; (8) no previous history of respiratory problems.

The exclusion criteria are: (1) acute myocardial infarction or acute heart failure; (2) acute pain on chest or abdominal; (3) with the clinical signs of significant pulmonary disease; (4) consciousness impaired; (5) patient with nasal feeding tube, tracheal tube and/or any condition, which prevent the measurement or training.

Recruitment of healthy participants:

The inclusion criteria are: (1) age ≥ 18 years; (2) had not undergone thoracic or abdominal surgery; (3) no previous history of respiratory problems.

The exclusion criteria are: (1) acute myocardial infarction or acute heart failure; (2) acute pain in the chest or abdominal; (3) with the clinical signs of significant pulmonary disease; (4) unstable hypertension, arrhythmias, or unstable cardiovascular conditions, such as fluctuations in blood pressure and heart rate, indicate poor cardiac prognosis or the need for vasopressor medications; (5) pregnant.

Ethical approval:

Ethical approval will be sought from the Research Ethics Committee of Hong Kong Metropolitan University and Shenzhen Second People's Hospital.

Sample size calculation:

Sample size calculation will be based on the use of repeated-measures analysis of variance (ANOVA) using the G*Power 3.1. Considering an effect size of 0.2, an alpha error probability of 0.05 and a power of 0.80, the estimated sample size is 54 participants. An additional 20% of the sample size will be included to account for attrition. The final estimated sample size will be at least 130 participants (65 for each cohort).

Procedure:

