After the baseline measurement, all participants will be requested to use a nose clip to hold the nose and breathe with the mouth through a pressure threshold inspiratory loading device (POWERbreathe, KH2, England). The inspiratory pressure will be set at 30%, 40%, 50%, 60%, 70%, or 80% of their MIP, in random order. Each MIP intensity protocol consists of 10 breaths. The procedure of IMT is followed by the published research protocols in people after stroke [28]. All MIP intensity protocols will be conducted in one day. A period of at least 10 minutes of rest time will be allowed between different protocols of contraction intensity (% MIP) on the same day [29].

Thickness of the left and right diaphragm (stroke and non-stroke), will be measured simultaneously by two identical ultrasonography at the end of maximum inspiration of 10 breaths of each MIP intensity protocol. The diaphragm thickness of both the left and right diaphragm at the end inspiratory breaths of the 10 breaths of each MIP intensity protocol will be recorded. Surface electromyography (sEMG) will be used to measure the activity of accessory muscle (sternocleidomastoid muscles) during each MIP intensity protocol. The % of MIP that associates with the highest calculated DTF and a relatively stable change in the activity of accessory muscles will be considered an appropriate training intensity for further IMT protocols.

The self-perceived exertion level will also be determined by the Rate of Perceived Exertion Borg scale at the end of each MIP intensity protocol [30].

All research procedures will be repeated again after 2 days to examine the test-retest reliability of ultrasonographic measurements of DTF.

Outcome measures:

[figure not shown]
Lung function

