Though various measures will be taken to minimize the risk of adverse event throughout the study, any adverse events that might happen will be recorded.

Statistical analysis:

All data will be reported as mean \pm standard deviation (SD) unless otherwise indicated. Demographic data and clinical characteristics for all participants will be summarized using descriptive statistics. Repeated-measures ANOVA will be used to compare the differences of DTF and sEMG parameters determined at each inspiratory pressure separately. Intraclass correlation coefficient will be used to determine the inter-rater reliability of two ultrasonic operators and examine the test-retest reliability coefficient of ultrasonographic measurements of DTF recorded with different inspiratory pressures.

P value will be set at 0.05. All data will be analyzed using the IBM SPSS Statistics for Windows, Version 25.0 (Armonk, NY: IBM Corp).

References:

1. Gbd, S., Global, regional, and national burden of stroke and its risk factors, 1990-2019: a systematic analysis for the Global Burden of Disease Study 2019. *Lancet Neurol*, 2021. 20(10): p. 795-820.
2. Wu, X., et al., The hospital costs of stroke patients in Chinese island populations: an 11-year tendency analysis. *J Stroke Cerebrovasc Dis*, 2015. 24(5): p. 988-992.
3. Feigin, V., et al., Global, Regional, and Country-Specific Lifetime Risks of Stroke, 1990 and 2016. *N Engl J Med*, 2018. 379(25): p. 2429-2437.
4. Li X and Z. X., Annual data set on national mortality surveillance 2018. Beijing: China Science and Technology Press, 2019.
5. Menezes, K.K., et al., Respiratory muscle training increases respiratory muscle strength and reduces respiratory complications after stroke: a systematic review. *J PHYSIOTHER*, 2016. 62(3): p. 138-44.
6. Liu, X., et al., Assessment of Diaphragm in Hemiplegic Patients after Stroke with Ultrasound and Its Correlation of Extremity Motor and Balance Function. *Brain Sciences*, 2022. 12(7): p. 882.
7. Lista-Paz, A., et al., Pulmonary function in patients with chronic stroke compared with a control group of healthy people matched by age and sex. *Physiother Theory Pract*, 2022: p. 1-9.
8. Wilson, R., Mortality and cost of pneumonia after stroke for different risk groups. *J Stroke Cerebrovasc Dis*, 2012. 21(1): p. 61-67.
9. Saposnik, G., et al., Variables associated with 7-day, 30-day, and 1-year fatality after ischemic stroke. *Stroke*, 2008. 39(8): p. 2318-2324.

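### The load choice depends partly on where sternocleidomastoid activity steepens, but the only planned sEMG analysis is an ANOVA of equal means, which ignores the order of the loads

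*Combined protocol and SAP*

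**What the plan says.** All references are to the combined protocol and SAP.

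- **Section 4, Procedure.** "The inspiratory pressure will be set at 30%, 40%, 50%, 60%, 70%, or 80% of their MIP, in random order". The load to carry forward is the one with the "highest calculated DTF and a relatively stable change in the activity of accessory muscles will be considered an appropriate training intensity". No threshold, reference load or statistic is attached to the accessory-muscle half of this rule.
- **Section 3, Introduction.** The motive is that, above diaphragm capacity, "the accessory respiratory muscle (in particular the sternocleidomastoid muscle) would be activated dramatically". The load named is 60% MIP, taken from healthy adults and people on mechanical ventilation.
- **Section 2, Abstract.** "Repeated-measures ANOVA will be used for statistical analysis to determine the most effective training intensity".
- **Section 4, Statistical analysis.** "Repeated-measures ANOVA will be used to compare the differences of DTF and sEMG parameters determined at each inspiratory pressure separately", at a P value of 0.05. No post-hoc comparison, trend contrast or change-point model is named. The intraclass correlations cover ultrasound only.

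**The concern.** The rule accepts some change in accessory activity, provided it is stable. Read with the Introduction, the question is whether activity climbs gradually or starts to climb disproportionately, and at which load.

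The planned test asks something else: whether mean sEMG is the same at all six loads. A gradual climb and an abrupt one both violate that null, so rejection does not tell them apart or point to a load. Half of the selection rule then has no planned analysis behind it, and the choice would rest on inspecting the means or on comparisons picked after seeing the data. The result is meant to inform later training protocols, so the basis for it should be stated beforehand.

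**Working it through.** **Inputs from the document.** Six loads (Procedure); 54 participants, and 65 per cohort after attrition (Sample size calculation); alpha 0.05 (Statistical analysis); effect size 0.2, read here as Cohen's f.

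**Assumed, because the document gives none.** Between-load correlation ρ of 0.5 to 0.85, exchangeable or autoregressive; normal data; SD 1 at every load.

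**1. The plan's own figure.** "Considering an effect size of 0.2, an alpha error probability of 0.05 and a power of 0.80, the estimated sample size is 54 participants". 54 × 1.2 = 64.8, so 65 per cohort and 130 in total reproduce. The 54 cannot be tied to one calculation, because the number of measurements, the correlation and the sphericity correction are not stated. Six loads with ρ = 0.5 and sphericity give 28; ρ = 0.2 with epsilon 0.75 gives 54. This is a separate matter. Only the values 54 and 65 are used below.

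**2. Why the F test ignores shape.** Under sphericity the noncentrality is λ = f² × n × 6 / (1 − ρ), where f is the SD of the six means divided by the within-load SD. Reordering or reshaping the means leaves λ unchanged if their variance is unchanged.

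- f = 0.2, n = 54, ρ = 0.5: λ = 0.04 × 54 × 6 / 0.5 = 25.92 on 5 and 265 df, power 98.6%.
- f = 0.2, n = 65: λ = 0.04 × 65 × 6 / 0.5 = 31.2 on 5 and 320 df, power 99.6%.
- f = 0.1, n = 54: λ = 0.01 × 54 × 6 / 0.5 = 6.48, power 45.7%.

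Simulated rejection at f = 0.2, n = 54 for three curves of equal variance:

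| Means at 30, 40, 50, 60, 70, 80% MIP | Rejects |
|---|---|
| straight line, 0 to 0.59 | 98.7% |
| step: 0, 0, 0, 0, 0.42, 0.42 | 98.8% |
| bend: 0, 0, 0, 0, 0.26, 0.52 | 98.5% |

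**3. Without sphericity.** Greenhouse-Geisser correction, n = 54 and 65, all the assumed correlations:

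| True curve | ANOVA rejects |
|---|---|
| steady rise, 0.5 SD in total | about 66% to 100% |
| steady rise, 1.0 SD in total | about 100% |
| 1.0 SD jump between any two adjacent loads | about 100% |

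**4. Unplanned step tests do not repair this.** There are 6 × 5 / 2 = 15 pairs. Adjacent-load tests at 0.05/15 flag each step of the steady 1.0 SD rise in only about 5% to 48% of trials. A large cumulative rise could thus look stable at most steps.

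**5. What does separate the patterns.** Take the five adjacent-load increments and subtract from each the mean of the other four.

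- Steady 1.0 SD rise: each increment is 0.2, so every difference is 0.2 − 0.2 = 0.
- 1.0 SD jump from 40% to 50%: increments 0, 1, 0, 0, 0. The jump step gives 1 − 0 = 1 and each other step gives 0 − 1/4 = −0.25. The same holds for a jump at any other step.

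**6. Why a slope change at 60% MIP cannot stand in for this.** Regressing on load and on the excess over 60% gives the slope-change weights (15, 2, −11, −24, −2, 20)/38.

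- Straight line: 0.
- 1.0 SD jump from 60% to 70%: (−2 + 20)/38 = 0.47.
- 1.0 SD jump from 50% to 60%: (−24 − 2 + 20)/38 = −0.16. It is significantly positive in about 0% of trials.
- 1.0 SD jump from 40% to 50%: (−11 − 24 − 2 + 20)/38 = −0.45. It is significantly negative in 95% to 100% of trials.
- Bend at 40%, then 0.25 SD per step: (−11 × 0.25 − 24 × 0.5 − 2 × 0.75 + 20 × 1)/38 = 0.10. It is detected in 13% to 55%.

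It works for a break where it is placed: 4% to 7% rejection under a steady rise, and 51% to 100% for a mild break at 60% (0.1 SD per step plus 0.25 SD extra per step above 60%).

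**7. Scale.** With an assumed log SD of 0.5, a constant-percentage rise (threefold from 30% to 80%) triggers the slope-change test in 43% to 99% of trials on the raw scale and 3% to 6% on the log scale. Steepening has no fixed meaning until the scale is fixed.

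**The case against.** **The criterion is undefined, so the steady-versus-jump hypothesis is a reading.** This stands. A plateau or little change would also fit the words. The point survives either reading: rejecting equal means does not identify a plateau, and failing to reject is not evidence of little change.

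**The plan never says that stability is decided by the ANOVA p-value, and means with SDs will be reported, so the profile will be visible.** Also true. A reader might infer that the investigators will treat a significant F as showing instability; the document does not say so. But the Abstract gives the ANOVA the task of determining the intensity, and no other route to the sEMG judgement is stated.

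**A reader might infer that the ANOVA has an inflated error rate.** It does not. Rejection under a steady rise is power against its own null, which is false in that case. Nor will it reject for every steady rise: at f = 0.1 with n = 54 power is only about 46%.

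**SPSS can produce trend contrasts.** It can, but the plan neither names one nor ties the criterion to one.

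**The stated aim is the strongest diaphragm thickening, and sEMG is only supporting.** This limits the weight of the point but does not remove it, because the selection rule uses both.

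**Conclusion.** The point holds as a mismatch between criterion and analysis. The accessory-muscle half of the rule concerns the shape of the load-sEMG curve, and the only planned analysis does not use load order. At the plan's own effect size (read as f = 0.2, with ρ = 0.5 and sphericity) it rejects about equally often, near 99%, for a line, a step and a bend. The simulated ranges rest on assumed correlations, normality and equal SDs. The insensitivity to order does not depend on the particular correlation chosen when that correlation is equal across loads.

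The document does not support going further. It does not show that a wrong load will be chosen or that the ANOVA is invalid as an overall test. It also does not show that 60% MIP is where activity breaks in people after stroke, since that figure is cited for other populations. This is a worthwhile, inexpensive clarification of the analysis and implies no view on which load is right.

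**What to change.** **Section 4, Statistical analysis.**

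- Keep the repeated-measures ANOVA as an overall test.
- Fix in advance which sEMG parameter and scale will be used, for example log or normalised amplitude.
- For the stroke cohort, report the five adjacent-load increments, and each increment's difference from the mean of the other four, with simultaneous 95% confidence intervals.
- A slope change at 60% MIP may be added as one supporting contrast, because the Introduction names that load. It must not define stability, since a jump at a lower load makes it negative and a bend at a lower load weakens it.

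**Section 4, Procedure.** Tie the stability criterion to these estimates and their confidence limits, and state how the limits will be read. Do not tie it to a significant or non-significant ANOVA or step test.

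**Cost.** A few sentences, with no new measurements, visits or participants; the estimates are within-person contrasts that run in the stated software. The main work is fixing the sEMG scale beforehand. Simultaneous intervals are wider and a mild break may remain unresolved: even the single slope-change contrast has only about 51% power in the least favourable setting tested for a mild break at 60%. That uncertainty should be reported as such.

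### The 0.05 level is not secured: the plan fixes no sphericity correction, confirmatory test or adjusted load comparisons, and its omnibus ANOVA cannot identify a best load

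*Combined protocol and SAP*

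**What the plan says.** The Procedure fixes the within-person factor: "The inspiratory pressure will be set at 30%, 40%, 50%, 60%, 70%, or 80% of their MIP, in random order". That is six ordered levels. Outcomes are taken on both sides of the body. For the diaphragm, "Thickness of the left and right diaphragm (stroke and non-stroke), will be measured simultaneously by two identical ultrasonography"; the sEMG electrodes are also bilateral. There are two cohorts, stroke and healthy.

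The whole inferential plan for the loads is one sentence in Statistical analysis, "Repeated-measures ANOVA will be used to compare the differences of DTF and sEMG parameters determined at each inspiratory pressure separately", followed by "P value will be set at 0.05". Nothing is said about sphericity, an epsilon correction, post-hoc comparisons, multiplicity, or a primary outcome, side or cohort for testing. Nor is it said how many ANOVAs will be run, or whether side and cohort enter one model as factors.

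Two other places bear on how the result will be used. The Abstract gives the ANOVA the task of finding which intensity works best. The Procedure takes forward the load with the greatest DTF, provided accessory-muscle activity stays fairly steady, and attaches no test to that choice.

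On size, the Sample size calculation says: "Considering an effect size of 0.2, an alpha error probability of 0.05 and a power of 0.80, the estimated sample size is 54 participants".

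**The concern.** Six loads in rising order are unlikely to satisfy sphericity, because neighbouring loads will probably resemble each other more than distant ones. An uncorrected F then rejects too often. SPSS prints corrected and uncorrected rows side by side, so a plan that does not name the deciding row leaves that choice until the data are seen.

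The second gap matters more. A significant F says only that some load differs from some other. To say which load is best, loads must be compared with each other: 6 × 5 / 2 = 15 pairs per outcome, side and cohort. The plan specifies no such comparisons, so it fixes no error rate for the conclusion it most wants to draw.

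At stake is the claim that one load is better than others when several are equivalent. The Procedure says the chosen load will inform later training protocols.

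**Working it through.** **1. The plan's own figure.** Inputs from Sample size calculation: f = 0.2 (taken as Cohen's f), alpha 0.05, power 0.80. For a within-person factor with m levels,

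λ = f² · N · m · ε / (1 − ρ), with df (m − 1)ε and (N − 1)(m − 1)ε.

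With m = 6, ρ = 0, ε = 1 and N = 54, λ = 0.04 × 54 × 6 = 12.96 on 5 and 265 df. Power is 79.5%, and 55 people reach 80%. So 54 is closely matched. Then 54 × 1.2 = 64.8, rounded to 65, and 65 × 2 = 130, as stated. The values of m, ρ and ε are not documented: ρ = 0.5 with six loads gives 28, and m = 2 with ρ = 0.5 gives 52.

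**2. Size of the omnibus F.** The documents give no covariance, so it is varied here. Simulated null data, n = 65, six loads:

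| Assumed covariance | ε | Uncorrected F rejects |
|---|---|---|
| Compound symmetry | 1.00 | 4.9% |
| AR(1) 0.5 | 0.77 | 6.4-6.7% |
| AR(1) 0.7 | 0.63 | 7.8% |
| AR(1) 0.9 | 0.50 | 9.2% |
| AR(1) 0.95 | 0.47 | 9.1-9.3% |
| AR(1) 0.5-0.9 plus independent measurement error (25-50% of the true variance) | – | 5.2-6.5% |

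If the SD also doubles from 30% to 80% MIP under AR(1) 0.5-0.9, the range is 7.0-9.8%. With n = 54, AR(1) 0.95 gives 9.5%. Greenhouse-Geisser gives 4.4-5.1% across the patterns tried.

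**3. Comparing loads.** Assume means of 0, 0.3, 0.6, 0.6, 0.6 and 0.6 SD, AR(1) 0.7 and n = 65. Four loads are equal, so 4 × 3 / 2 = 6 pairs are truly null. The uncorrected F is significant in about 99% of trials, so requiring it first gives almost no protection. A false difference among the four equal loads follows in about 20% of trials, and in 20-21% under compound symmetry or with added measurement error. The large-sample studentized range gives the same figure: P(Q₄ > 1.96√2) = 20.3%. Holm over all 15 pairs brings it to 2-3%. With five loads equal, the unadjusted rate is 26-29%.

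If no load differs at all, pairs tested only after a significant F err no more often than the F itself (5-9%). Pairs tested regardless of the F err in 31-37% of trials.

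**4. Several ANOVAs.** Two outcomes × two sides × two cohorts give at most 8 load curves. For k independent tests at 5%, the chance of at least one false result is 1 − 0.95^k:
- k = 2: 9.8%
- k = 4: 18.5%
- k = 8: 33.7%

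For eight tests with correlated sides and outcomes (assumed 0.5 and 0.3, up to 0.8 and 0.5), it is:
- 28-30% uncorrected under compound symmetry
- 37-50% uncorrected under AR(1) 0.7-0.9
- 24-30% with Greenhouse-Geisser

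**5. The selection rule.** In the four-equal-loads case the highest sample mean always fell on one of the four, with 21-30% for each. Neither Greenhouse-Geisser nor Holm changes which load has the highest mean, so correcting the tests alone would not stop one of several equivalent loads being named best.

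**The case against.** A reader might infer that the 0.05 level is definitely breached: that the omnibus test runs at 7-10% and that false claims reach a third or more. The documents do not support that.

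- They never say that the uncorrected row will decide or that pairs will go unadjusted. Both are inferred from silence.
- The 7-10% range needs strong serial correlation without separate measurement error. Each load has its own ultrasound readings, so some independent error is likely, and it pulls the rate back towards 5%.
- A third needs eight independent ANOVAs, or pairs tested whatever the F shows. The plan does not say eight are run. Both sides are measured in the same people at the same time, so independence fails. The two mechanisms also do not simply add.
- The Aims name one outcome in one population, DTF after stroke. The Procedure requires high DTF together with steady accessory-muscle activity, which is a joint condition and not eight alternative routes to success.
- The load is picked by the highest DTF and not by a p-value.

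All of this limits the size of the problem, but none of it supplies the missing rule. The 20% result for partly equal loads needs neither a failure of sphericity nor a complete null, and it survives a significant F. The last point shows a further gap: a bare maximum of six means has no error control, and the Abstract assigns the same decision to the ANOVA.

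**Conclusion.** The point holds in this form: the plan does not show how 0.05 is controlled, and its named test cannot answer its main question. The omnibus inflation is modest and uncertain, from none to about double the nominal level depending on covariance. The firmer figure is the roughly one-in-five chance of falsely separating loads that are equal. It assumes that four of six loads are equal, that the others differ enough for the F to be significant, and that pairs are compared unadjusted. The risk across outcomes, sides and cohorts, 10-19% for two to four independent tests and 24-50% for eight correlated ones, applies only if they are analysed as separate ANOVAs. This should be settled before analysis, because the choices left open determine what the study can claim.

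**What to change.** In Statistical analysis:

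1. State that the Greenhouse-Geisser corrected test decides in every repeated-measures ANOVA.
2. Name one confirmatory analysis that matches the Aims: DTF in the stroke cohort, on one side fixed in advance, for example the affected side. Which side is for the investigators to choose; it has to be fixed beforehand.
3. Within it, compare loads pairwise with Holm adjustment over all 15 pairs.
4. Label sEMG, the other side and the healthy cohort as secondary, reported with confidence intervals.

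In Procedure, tie the selection rule to these comparisons. Report the load with the highest mean DTF together with every load not distinguishable from it after Holm adjustment. Claim a single best load only if it is separated from the others.

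No new data are needed, but there is a power cost. For large effects it is small: in the four-equal-loads case, omnibus power falls from 99.2% to about 98.4%. At the plan's f = 0.2 it may not be. If 54 rested on ρ = 0 and ε = 1, the same formula gives 71% power at ε = 0.77 and 55% at ε = 0.47, down from 79.5%. Positive correlation works the other way: ρ = 0.5 with ε = 0.5 gives 87.9% at 54. The Sample size calculation should therefore state the number of measurements, ρ and ε it assumed, and restate power accordingly.
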